#### 4.3.1 Lost to Follow-Up

A patient will be considered lost to follow-up if he/she repeatedly fails to return for scheduled visits and is unable to be contacted by the study site.

The following actions must be taken if a patient fails to return to the study site for a required study visit:

- The study site must attempt to contact the patient and reschedule the missed visit as soon as possible, counsel the patient on the importance of maintaining the assigned visit schedule, and ascertain whether or not the patient wishes to and/or should continue in the study.
- Before a patient is deemed lost to follow-up, the Investigator or designee must make every effort to regain contact with the patient (where possible, 3 telephone calls and, if necessary, a certified letter to the patient's last known mailing address or local equivalent methods). These contact attempts should be documented in the patient's medical record.

Should the patient continue to be unreachable, he/she will be considered to be lost to follow-up.

#### 4.3.2 Termination of Study

Although the Sponsor has every intention of completing the study, the Sponsor may terminate the study at any time for clinical or administrative reasons.

#### 4.3.3 Screening Failures

Screening failures are defined as patients who consent to participate in the clinical study but are not subsequently randomized into the study. A minimal set of screening failure information is required to ensure transparent reporting of screening failure patients to meet the Consolidated Standards of Reporting Trials publishing requirements and to respond to queries from regulatory authorities. Minimal information includes demography, screening failure details, eligibility criteria, and any SAE(s).

Patients who do not meet criteria for participation in the study (screen failure) may be rescreened at the discretion of the Medical Monitor. The Medical Monitor will clearly document the rationale for any rescreening decision. Rescreened patients will be assigned a new screening number, be reconsented, and may have screening assessments repeated if necessary.

## 5 STUDY TREATMENTS

### 5.1 Treatment Groups

Eligible patients with glenohumeral OA or shoulder AC will be randomized in a 1:1 ratio within their shoulder condition (OA or AC) and treated in the following arms:

- Nominal 32 mg FX006 as a 5 mL IA injection to the index shoulder
- Placebo (sterile normal saline) as a 5 mL IA injection to the index shoulder

### 5.2 Rationale for Dosing

FX006 at IA doses up to 60 mg has been tested in knee OA patients with an acceptable safety profile. FX006 has been approved to treat knee OA pain at a dose of 32 mg. The glenohumeral joint is also a large synovial joint. Similar doses of conventional corticosteroids have been used for the glenohumeral joint as in the knee joint. Likewise, the same dose of FX006 for the glenohumeral joint as for the knee joint is reasonable, particularly as the FX006 formulation results in much lower drug exposure to joint tissues. Therefore, a 32 mg IA dose has been selected for glenohumeral OA or shoulder AC.

### 5.3 Randomization and Blinding

Patients from each shoulder condition will be randomized on Day 1 to 1 of 2 treatment arms (FX006 or placebo) using centralized randomization accessed through an interactive voice/web response system randomization (IxRS) module.

Glenohumeral OA patients will be stratified by the Baseline average daily shoulder pain with movement score (0 to 10 NRS) (5.0 to <7.0 or ≥7.0 to 9.0). Shoulder AC patients will be stratified by the Baseline average daily shoulder pain with movement score (0 to 10 NRS) (5.0 to <7.0 or ≥7.0 to 9.0) and pain duration since onset at Screening (1 to 3 months, inclusive, or >3 to ≤6 months).

The blinded-assessor technique will be used in this study to maintain double-blind conditions. Key study site staff roles are defined below and a site-specific blinding plan will be developed to ensure the blind is maintained throughout the duration of the study. Treatments will be prepared by an unblinded pharmacist/coordinator who has experience with the preparation of study medication and who has been properly trained by the Sponsor or designee. Intra-articular injections will be performed by an unblinded injector.

#### **Overall unblinded team responsibilities may include the following:**

- Will have no other contact with the patient and will not have any blinded roles in the study (the only exception is that the unblinded injector may be delegated the role of obtaining informed consent at the Screening Visit).
- Will not share treatment assignments with the blinded assessor, the patient, other blinded study personnel, or Sponsor personnel/representatives.

- Will make every effort to maintain the blind (e.g., reconstitute the study medication in an isolated room to prevent others from seeing and hearing tapping process).
  - If an adverse event occurs during the injection procedure, the unblinded injector will record the details of the adverse event in the patient's chart and provide a full report of the event to the blinded assessor in a blinded manner.

**Detailed responsibilities for the unblinded study site staff may include the following:**

- **Unblinded pharmacist/coordinator**

- Will receive the randomization notification of the patient's study medication
- Will dispense the appropriate prepared study medication and necessary materials for the injection
- Will perform study medication reconstitution
- Will transport the assigned treatment to the location where injection will take place
- Will ensure that the FX006 investigational product is resuspended prior to injection
- Will ensure the blind is maintained by following the site-specific blinding plan to ensure the patient is unaware of the treatment assignment prepared for injection
- Will remain with the patient and unblinded injector until the injection is completed
- Will record details of study medication preparation, transport (if applicable), and administration
- Will store the used vials in the study medication storage location to be held until study medication accountability is performed by the unblinded monitor
- Will complete the study medication accountability logs

Note: Depending on site-specific requirements, the unblinded pharmacist/coordinator may be split into 2 roles. Details will be specified in the site-specific blinding plan.

- **Unblinded injector**

- Will perform study medication reconstitution (if not completed by the unblinded pharmacist/coordinator)
- Will ensure that the FX006 investigational product is resuspended prior to injection
- Will perform the aspiration and injection of the index shoulder using ultrasound in accordance with both his/her experience and the protocol-specified procedure

The unblinded pharmacist/coordinator will report any product-related issues relating to reconstitution or administration of FX006 according to Sponsor instructions located in the Unblinded Pharmacy Manual.

All other study site and Sponsor personnel/representatives involved in the study at the study site will be blinded with regards to the study medication being administered with the following Sponsor/representative exceptions:

- **Unblinded monitor(s)**
  - Will be responsible for unblinded study site monitoring
  - Will perform study medication accountability (used and unused vials)
- **Unblinded clinical trial manager**
  - Will be responsible for oversight of unblinded study site monitoring
  - Will review unblinded monitoring visit reports and escalate unblinded study site issues to unblinded Sponsor representative
- **Unblinded Sponsor representative**
  - Will be the point of escalation for the unblinded team
  - Will address any product-related issues
  - Will escalate, in a blinded manner, to the blinded study team, if necessary
- **Sponsor regulatory and pharmacovigilance personnel for safety assessment and reporting, if necessary**

Information regarding treatment assignments will be kept secure by the Sponsor or designee, per standard operating procedures.

#### **5.4 Breaking the Blind**

Investigators are not to break the study treatment blind except when information concerning the study medication is necessary for the medical treatment of the patient. If a medical emergency requiring unblinding occurs, the Investigator (or designated physician) is strongly encouraged to contact the medical or safety monitor to assess the necessity of breaking the study medication blind.

If unblinding is warranted, the Investigator will obtain the treatment assignment information from the IxRS. Every effort is to be made to limit study site personnel unblinding only to those individuals providing direct care to that patient.

Any intentional or unintentional breaking of the blind is to be reported immediately to the Sponsor that unblinding has occurred, without revealing the treatment. The other circumstances in which unblinding may be necessary are at the request of a patient who becomes pregnant during the study, or for regulatory reporting purposes.

If the blind is broken, the date, time, and reason must be recorded in the patient's eCRF, and any associated SAE report, if applicable.

## 5.5 Drug Supplies

### 5.5.1 Formulation and Packaging

FX006 is an extended-release formulation of TA in 75:25 PLGA microspheres. FX006 will be supplied as a sterile, white to off-white powder in a single unit dose 5 mL vial with a butyl rubber stopper, aluminum seal, and plastic cap. FX006 will be reconstituted in diluent that will be supplied as a sterile aqueous solution in a 5 mL vial with a butyl rubber stopper, aluminum seal, and plastic cap.

Placebo (NaCl injection, USP) is a sterile, nonpyrogenic, isotonic solution of NaCl and water for injection.

Instructions for shipment, storage, accountability, reconciliation, and destruction of study medication are provided in the Unblinded Pharmacy Manual.

### 5.5.2 Study Medication Preparation and Dispensing

Dispensing, preparation, and administration of investigational products will occur under the supervision of the Principal Investigator. The Principal Investigator may only delegate these activities in accordance with state licensing board requirements, local institutional policies, and applicable law. Before delegating this activity, the Principal Investigator should also ensure that the delegate is trained on and understands the requirements of the protocol.

Immediately prior to IA injection, FX006 will be reconstituted in 5 mL of a diluent containing an isotonic, sterile aqueous solution of NaCl (0.9% w/w), CMC (0.5% w/w), and polysorbate-80 (0.1% w/w) to form a suspension prior to IA injection.

The reconstitution process should not be witnessed by any blinded study staff or by the patients.

Refer to the Unblinded Pharmacy Manual for detailed instructions on study medication preparation and IA administration.

### 5.5.3 Study Medication Administration

Only patients enrolled in the study may receive study medication and only authorized site staff may supply or administer study medication.

Any difficulties with the study medication administration should not be reported to the blinded assessor unless it is a direct cause of an adverse event. In the event of difficulties during the procedure with administering the study medication, please proceed as follows:

- Stop the procedure.
- Do not attempt to reinject.
- Report the event to the unblinded coordinators at the site and to the unblinded team at Flexion Therapeutics, Inc. via the Product Complaint Form.
- The patient and blinded study personnel (coordinators and Investigators) should not be informed the procedure was stopped.

#### 5.5.3.1 Index shoulder aspiration

Aspiration must be attempted prior to injection of study medication on Day 1. If effusion is detected by ultrasound guidance, the injector must withdraw to near dryness prior to the injection.

Refer to the Unblinded Pharmacy Manual for detailed instructions on study medication preparation and IA administration.

#### 5.5.4 Treatment Compliance

Study medication will be administered by the unblinded injector in the clinic. Details regarding study medication administration will be documented in the eCRF. The receipt, dispensation, and return/destruction of any study medication will be properly documented.

If for any reason the administration of study medication is stopped before the entire volume is injected, the injector should document the reason for stopping administration.

#### 5.5.5 Storage and Accountability

The packaged kits of FX006 must be stored under refrigeration at 2°C to 8°C in a secure, environmentally controlled, and monitored (manual or automated) area in accordance with the labeled storage conditions with access limited to authorized, unblinded site staff.

Placebo will be stored according to the commercial label and USP guidelines in a secure, environmentally controlled, and monitored (manual or automated) area in accordance with the labeled storage conditions with access limited to the authorized, unblinded site staff.

The Investigator, or designee, must confirm appropriate temperature conditions have been maintained during transit for all study medications received and any discrepancies must be reported and resolved before the use of study medication. Any temperature excursions should be documented according to the Unblinded Pharmacy Manual instructions for Sponsor assessment and authorization for continued use.

All study medication required for completion of this study will be provided by the Sponsor or designee.

The Investigator, site, or the head of the site (where applicable) is responsible for study medication accountability, reconciliation, and record maintenance (i.e., receipt, reconciliation, and final disposition of records).

In the event of a product complaint, complete the Product Complaint Form located in the Unblinded Pharmacy Manual.

#### 5.5.6 Rescue Medication

The study site will supply rescue pain medication (acetaminophen) that will be provided by the Sponsor. At the site, the rescue medication should be stored according to the commercial label. To standardize pain relief rescue medication across all patients, starting at the Screening Visit, patients will discontinue all excluded or restricted medications and observe the following procedures:

- The designated rescue medication is acetaminophen 500 mg. The recommended dosing is 2 tablets every 6 hours as needed, up to a maximum of 6 tablets (3000 mg) per 24-hour period.

- Starting at the Screening Visit, each patient will be provided with a sufficient quantity of rescue medication for the interval to the next scheduled study site visit.
- Patients will record their dosage regimen of the rescue medication over the past 24 hours daily in their eDiary.

At each visit, patients will return any unused rescue medication provided at the previous visit for rescue medication accountability and be issued a new supply.

As with FX006/placebo, the Investigator, site, or the head of the site (where applicable) is responsible for rescue medication accountability, reconciliation, and record maintenance (i.e., receipt, reconciliation, and final disposition of records).

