#### **4.2 Exclusion Criteria**

A patient who meets any of the following criteria will be excluded from participation in the study:

1. Is unable to washout from excluded (see Section 5.6.1) or restricted medications (see Section 5.6.2).
2. Has both glenohumeral OA and shoulder AC.
3. Has bilateral AC.
4. Has bilateral glenohumeral OA with glenohumeral OA pain of the shoulder contralateral to the index shoulder  $>3.0$  (0 to 10 NRS) within 1 month prior to the Screening Visit (patient self-report acceptable).
5. Has a history of symptomatic arthritis in other joints of the index shoulder (e.g., acromioclavicular joint or scapulothoracic joint), as confirmed by medical history and physical examination.
6. Has a history or suspicion of full thickness rotator cuff tear in the index shoulder as assessed by the Investigator per medical history and physical examination, ultrasound, or magnetic resonance imaging (MRI) obtained within 6 months of the Screening Visit.
7. Has symptomatic partial rotator cuff tear, tendinopathy, tendonitis, or bursitis in the index shoulder as assessed by Investigator per medical history and physical examination, ultrasound, or MRI obtained within 6 months of the Screening Visit.
8. Has a subchondral bone insufficiency fracture or humeral head necrosis/collapse in the index shoulder based on X-ray used for study qualification.
9. Shoulder AC patients only: Has a history of shoulder surgery in the index shoulder or radiotherapy (e.g., for breast, neck, or upper limb tumors).
10. Glenohumeral OA patients only: Has a previous shoulder injury in the index shoulder with functional limitation  $\geq 1$  month (e.g., dislocation or fracture) or surgery in the index shoulder (including clavicle or scapula) within 52 weeks prior to the Screening Visit.

11. Has an index shoulder with major dysplasia or congenital abnormality, osteochondritis dissecans, acromegaly, ochronosis, hemochromatosis, Wilson's disease, primary osteochondromatosis, or a history of avascular necrosis with secondary OA.
12. Has current or history of infection (e.g., osteomyelitis) in the index shoulder or current skin infection at injection site.

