### **5.6.1 Excluded Medications and/or Procedures**

The following medications are excluded for the duration of the study. If a patient is taking any of these excluded medications, they must, after signing the ICF, complete a washout consisting of a period of 5 half-lives of the excluded drug 7 days prior to Day 1.

- Oral nonsteroidal anti-inflammatory drugs (NSAIDs).
- Aspirin (>325 mg/day).
- Centrally-acting pain medications (e.g., pregabalin, gabapentin, duloxetine, and/or milnacipran) unless specifically allowed, or allowed with restriction, in the protocol.
- Opioids.
- Topical therapies (e.g., NSAIDs, capsaicin, lidocaine patches, CBD products, or other local treatments) applied to the index shoulder.
- Anesthetic medications injected locally in the index shoulder (other than the selected anesthetic if used for the IA injection procedure).
- Muscle relaxants (e.g., cyclobenzaprine, tetrazepam, and/or diazepam).

The following medications and/or procedures should not be taken and/or performed throughout the study:

- IV or IM corticosteroids within 3 months of the Screening Visit.
- Oral corticosteroids within 1 month of the Screening Visit.
- Inhaled, intranasal, or topical corticosteroids within 2 weeks of the Screening Visit.
- IA corticosteroids in any joint within 3 months of the Screening Visit.
- IA viscosupplementation (hyaluronic acid) or any IA intervention (e.g., IA injection) in the index shoulder within 6 months of the Screening Visit.

- Any investigational drug, biologic, or device within 3 months of the Screening Visit.
- Chemotherapeutic agents, immunomodulators, or immunosuppressants other than corticosteroids within 5 years of the Screening Visit.
- Live or live-attenuated vaccines within 3 months of the Screening Visit.
- Significant changes with regard to physical activity and lifestyle, within 1 month prior to the Screening Visit and changes throughout the duration of the study.

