#### 5.6.2 Restricted Medications and/or Procedures

The following medications/nonpharmacologic therapies may be taken or used throughout the study with the following restrictions:

- Aspirin for cardioprotection at a maximum dose of 325 mg/day provided the dose has been stable over the 3 months prior to study entry.
- Medical therapy for depression, including selective serotonin reuptake inhibitors, non-selective serotonin reuptake inhibitors, serotonin and norepinephrine reuptake inhibitors, and tricyclic antidepressants provided the dose has been stable over the 3-month period prior to the Screening Visit (see Appendix E).

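### Section 5.5.6 tells patients to stop restricted medications from Screening, but Section 5.6.2 allows those same medications for the whole study; Exclusion 1 adds to the ambiguity

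*Combined protocol and SAP*

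**What the plan says.** Four places in the protocol bear on this.

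- **Section 5.5.6 (Rescue Medication).** After the purpose clause "To standardize pain relief rescue medication across all patients", the instruction is that "starting at the Screening Visit, patients will discontinue all excluded or restricted medications".
- **Section 4.2, Exclusion 1.** A patient is excluded who "Is unable to washout from excluded (see Section 5.6.1) or restricted medications (see Section 5.6.2".
- **Section 5.6.2 (Restricted Medications and/or Procedures).** The section opens: "The following medications/nonpharmacologic therapies may be taken or used throughout the study with the following restrictions". It has two entries. The first is "Aspirin for cardioprotection at a maximum dose of 325 mg/day provided the dose has been stable over the 3 months prior to study entry". The second covers drug treatment for depression in several classes, ending with "tricyclic antidepressants provided the dose has been stable over the 3-month period prior to the Screening Visit (see Appendix E".
- **Section 5.6.1 (Excluded Medications and/or Procedures).** Aspirin is excluded only at the higher dose: "Aspirin (>325 mg/day". Centrally acting pain medications are excluded "unless specifically allowed, or allowed with restriction, in the protocol".

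Three other places deal with washout: Inclusion 7, the Screening procedures in Section 6.3, and footnote 11 to Table 1 in Appendix A. All three name excluded medications only and say nothing about restricted ones.

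**The concern.** Section 5.6.2 is the only place that defines restricted medications, and it lists only aspirin and antidepressants. The instruction in Section 5.5.6 therefore has nothing else to refer to. It tells patients to stop what the dedicated medication section lets them continue.

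What is at stake is patient safety and consistent eligibility. A site that follows 5.5.6 to the letter could stop cardioprotective aspirin or a stable antidepressant at Screening, and the text gives no taper or supervision step. A site that follows 5.6.2 would leave the drug alone. About 35 sites will apply the text, so instructions and eligibility decisions could differ between them.

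The existing safeguards would catch this only in part. Section 5.6.4 requires medication changes and their reasons to be recorded, so a stop would appear in the eCRF. It would not stand out as a departure from protocol, because 5.5.6 calls for it. Adverse events are assessed at every visit, but the PHQ-9 is scheduled at Screening only and would not be repeated after an antidepressant was stopped.

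**Working it through.** The plan states no figure on this point and no arithmetic applies. The check is to take four kinds of patient through the current rules.

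| Patient at Screening | Section 5.6.2 | Section 5.6.1 | Section 5.5.6 | Exclusion 1, read literally |
|---|---|---|---|---|
| A. Cardioprotective aspirin, up to 325 mg/day, stable for 3 months | Continue | Not excluded | Stop | Ineligible if unable to wash out |
| B. Antidepressant for depression, dose stable for 3 months | Continue | Exempt where allowed with restriction | Stop | Ineligible if unable to wash out |
| C. Antidepressant, dose changed within the 3 months | Condition not met | No exemption through 5.6.2 | Stop | Ineligible if unable to wash out |
| D. Aspirin above 325 mg/day | Above the cap | Excluded, wash out | Stop | Ineligible if unable to wash out |

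1. For A and B, 5.6.2 and 5.5.6 give opposite instructions. This is a direct contradiction between operative rules.
2. For A and B, 5.6.1 sides with 5.6.2. Its aspirin threshold starts where the 5.6.2 allowance ends, and it gives way to restricted use for centrally acting drugs.
3. The 3-month stability conditions also point to 5.6.2 as the intended rule. Requiring a stable dose has little purpose if the drug is to be stopped at Screening.
4. The purpose clause in 5.5.6 explains why the instruction is given, but it does not narrow the word *all* to analgesics.
5. Exclusion 1 allows two readings. Its pointer to 5.6.2 may mean that only use outside the 5.6.2 conditions has to be washed out, in which case A and B are unaffected. Without that qualifier, it can also be applied to A and B. This is ambiguity, a weaker fault than the contradiction in step 1.
6. For D, the rules agree on stopping and there is nothing to repair.
7. For C, the current text points towards stopping the drug in order to qualify. Section 5.6.1 sets a washout (5 half-lives, completed 7 days before Day 1) for excluded medications. None is stated for restricted ones.

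**The case against.** The best reply is that sites would work out what is meant. The washout steps they carry out at Screening (Inclusion 7, Section 6.3, Table 1 footnote 11) name excluded medications only. Sections 5.6.1 and 5.6.2 are the dedicated medication rules and give specific doses and stability periods. The conflicting words sit in a section about rescue analgesia. Exclusion 16 also seems to use *restricted medication* loosely, to mean one that is not allowed, which suggests careless terminology more than a second rule. Exclusion 1 cites 5.6.2, and that citation leads the reader to the conditions for permitted use.

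Much of this stands. It lowers the likelihood that permitted drugs would actually be stopped, and it is why Exclusion 1 should be called ambiguous and not a second flat contradiction. It does not remove the conflict in 5.5.6, which is a direct instruction about patients' medication and carries no qualifier. That sites may guess the intent correctly is a reason to correct the wording.

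A reader might also go further and borrow the 5.6.1 washout for Exclusion 1: a 21-day Screening maximum less 7 days leaves 14 days, and 14 / 5 = 2.8 days would be the longest half-life that could be cleared. The documents do not support this. They apply that washout to excluded medications only, they give no half-lives, and Section 4.3.3 allows rescreening at the Medical Monitor's discretion. The figure does not measure impact.

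**Conclusion.** The contradiction between Section 5.5.6 and Section 5.6.2 is real and present in the current text, and it should be fixed. Exclusion 1 compounds it by leaving its scope open.

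The drugs affected are cardioprotective aspirin up to 325 mg/day and antidepressants, each at a dose stable for 3 months. The number of patients is unknown, because the documents do not give the share of screened patients who take these drugs. The consequences described depend on a site reading 5.5.6 or Exclusion 1 literally; nothing in the documents shows that any site would.

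A reader might infer that stopping these drugs would bias the primary analysis. That does not follow: a stop at Screening comes before randomization, under the same rule in both arms. Sample size, power and type I error are unaffected. The point rests on patient safety and consistent eligibility alone.

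**What to change.** Two wording changes.

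1. In Section 5.5.6, delete the words *or restricted*, so that the instruction covers excluded medications only.
2. Reword Exclusion 1 to: *Is unable to wash out from excluded medications (see Section 5.6.1), or is using a restricted medication outside the conditions of Section 5.6.2.*

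With these changes, patients A and B continue their drug and can enter. Patient C is not eligible at that time, is not told to stop the drug, and may be rescreened under Section 4.3.3 once the dose has been stable for long enough. Patient D is handled as now: aspirin above 325 mg/day remains an excluded medication with the 5.6.1 washout.

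A washout rule for restricted medications should not be added to Section 5.6.2. It would direct patients to come off a recently started or adjusted antidepressant or cardioprotective aspirin in order to qualify, which is the harm the change is meant to prevent.

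The cost is a short amendment, which needs IRB approval before implementation (Sections 11.9 and 12.1), and a clarification letter to about 35 sites. No extra patients, visits or data are needed.
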